1.1 Study Design Diagram

1.2 Study Flow Chart

Study Assessment/Procedure	Screening ¹⁰	Enrollment	Always in Hospital				Post-Treatment Follow-up			
			Immediately Prior to Study Drug Infusion ¹¹	Immediately Post Study Drug Infusion	Post Cardiac Cath ± PCI ¹⁴	24 Hours (±2) Post Start of Study Drug or Discharge ^{17,18}	14 days (± 5) Post Study Drug Infusion Office Visit	30 days (± 5) Post Study Drug Infusion Phone Call	90 days (± 7) Post Study Drug Infusion Phone Call	
Explain Study / Written Informed Consent(s) ¹	X									
Review of Inclusion/Exclusion Criteria	X									
Medical History ² and Demographics	X									
Physical Examination	X					X ¹⁹	X			
Electrocardiogram (12-Lead ECG)	X				X		X			
Vital Signs ³ Assessment	X		X	X	X	X	X			
Previous and Concomitant Medications	X	←—————→								
Adverse Events Assessment (Bleeding and Non-Bleeding)		←————— X —————→								
Serious Adverse Events Assessment (Bleeding and Non-Bleeding)		←————— X —————→								
Clinical Efficacy Endpoint Events Assessment (MACE, Stent Thrombosis)		←————— X —————→								
Standard Local Laboratory Tests:										
Hematology ⁴	X				X	X	X			
Serum Chemistry ⁵	X					X				
PT/INR, aPTT	X					X				
Activated Clotting Time					X ¹⁵					
Lipid Panel ⁶	X									
Hemoglobin A1c	X									
Pregnancy Test ⁷ (urine)	X		X ⁷				X			

Study Assessment/Procedure	Screening ¹⁰	Enrollment	Always in Hospital				Post-Treatment Follow-up			
			Immediately Prior to Study Drug Infusion ¹¹	Immediately Post Study Drug Infusion	Post Cardiac Cath ± PCI ¹⁴	24 Hours (±2) Post Start of Study Drug or Discharge ^{17, 18}	14 days (± 5) Post Study Drug Infusion Office Visit	30 days (± 5) Post Study Drug Infusion Phone Call	90 days (± 7) Post Study Drug Infusion Phone Call	
Sample Collections For Research (required):										
Cardiac Troponin I ⁸ Serum			X		X ¹⁶	X ¹⁶				
Sample Collections For Research (optional ¹):										
Pharmacodynamics (PD)- Platelet Aggregation ⁹ Whole Blood			X	X ¹²		X ^{12, 20}	X			
Pharmacokinetics (PK) ⁹ Plasma			X	X ¹²		X ^{12, 20}	X			
Exploratory Biomarkers Plasma			X	X ¹³		X ^{13, 20}	X			
Pharmacogenomics (DNA/RNA) Whole Blood			X							
Randomization		X								

- Written informed consent for the optional sampling: pharmacogenomics (DNA/RNA), pharmacodynamics-platelet aggregation, pharmacokinetics, and exploratory biomarkers may be contained in the same instrument as written informed consent for the rest of the study, or may be a separate document, at the discretion of the institutional review board (IRB). Regardless, separate signatures of informed consent are required to collect each of the optional samples.
- Including subject's cardiac history, the clinical evaluation leading to the cardiac catheterization procedure (i.e., CAD presentation, Canadian Cardiovascular Society Classification for angina, Thrombolysis in Myocardial Infarction Risk Score for UA/NSTEMI, and New York Heart Association Classification of Functional Status for heart failure), bleeding history and allergy history (drugs, IV contrast media, food, stings and atopic conditions and any required treatment/medical intervention).
- Vital signs to include heart rate, blood pressure, and at Screening only, height and weight.
- Hematology includes a complete blood cell count, differential WBC count and platelet count.
- Chemistry includes sodium, potassium, chloride, carbon dioxide, glucose, BUN, creatinine, alkaline phosphatase, total bilirubin, ALT and AST.
- Lipid Panel includes total cholesterol, high-density lipoprotein cholesterol, calculated low-density lipoprotein cholesterol and triglycerides (does not have to be fasting).
- Urine pregnancy test (urine beta-HCG) must be performed on all women of child-bearing potential prior to randomization and must also be repeated prior to study drug administration if screening assessment >24 hours.

8. Cardiac Troponin I (cTnI) analysis to be conducted by a centralized lab at Tufts Medical Center. Additional cardiac biomarkers (i.e., Troponin I or T, CK-MB) analyzed locally at the clinical site for routine management of the subject will be guided by standard of care/local hospital clinical practice and the results will be collected when applicable.
9. At select sites only in the Sub-study.
10. Screening evaluations must be performed prior to Enrollment/Randomization and must be within 14 days prior to cardiac catheterization and study drug treatment (may include standard of care preadmission testing for the planned procedure).
11. Study drug infusion must be started within 0-60 min prior to the commencement of the cardiac catheterization procedure (diagnostic angiography).
12. Samples will be collected at 30 min \pm 5 min, 1 h \pm 5 min, 2 h + 15 min (immediately after completion of infusion), 6 h – 2 h (4 to 6 h) and 24 h \pm 2 h (or at hospital discharge, whichever occurs sooner) after the start of the study drug infusion (T=0).
13. Samples will be collected at 2 h + 15 min (i.e., immediately after completion of infusion), 6 h – 2 h (4 to 6 h) and 24 h \pm 2 h (or at hospital discharge, whichever occurs sooner) after the start of the study drug infusion (T=0).
14. After cardiac catheterization, if PCI does not commence or after PCI commences, regardless of outcome. Except as specifically noted, timing should be consistent with standard practice at the clinical site.
15. Following administration of the initial bolus of anticoagulant (UFH/LMWH), activated clotting time will be measured locally at “peak dose” and just prior to sheath removal, as well as according to the standard of care and applies only to PCI subjects.
16. Collect samples for research cTnI at 4 to 8 h and 12 to 24 h after completion of PCI. In addition, collect samples immediately after occurrence of symptoms suggestive of acute coronary syndrome, and again 4 to 8 h and 12 to 24 h after symptoms if the subject has not yet been discharged from the hospital.
17. Assessments should be performed at 24 Hours (\pm 2 h) post start of study drug infusion or just prior to Discharge, whichever occurs sooner.
18. If a subject remains in the hospital for >24 hours, additional testing/evaluation will be guided by standard of care and local guidelines.
19. The clinical site’s standard of care, cardiac catheterization nursing assessment may be performed to evaluate the subject’s clinical status in lieu of a complete physical exam at the 24 hour/Discharge (whichever occurs sooner) time point.
20. After the 24 hour collection, if a subject remains in the hospital for \geq 48 h, collect an additional sample at discharge.

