platelet agent during PCI as discussed above. The subgroup of subjects on concomitant ASA therapy revealed stronger apparent effects of PZ-128 on inhibition of maximal and final aggregation to 8 μM ($P=0.084$) and 12 μM ($P=0.06$) SFLLRN in the 0.5 mg/kg dose cohort. The subgroup of subjects receiving ASA in the 0.5 mg/kg dose cohort had 60-80% average inhibition of final aggregation to 8 μM SFLLRN at 30 min-2 h and 100% inhibition by 6 h. There was 40% of recovery to aggregation to 8 μM PAR1 agonist by 24 h and 60% recovery by 192 h (the next sampling time point). Higher concentrations of PAR1 agonist (e.g., 20 μM SFLLRN) showed 80% recovery of aggregation by 24 h and 95% by 192 h in the 0.5 mg/kg dose cohort receiving concomitant ASA. At high doses of 1-2 mg/kg, PZ-128 gave significant mean ~90-100% inhibition at 1-2 h time points regardless of whether the subjects received ASA or not.

[figure not shown]
At 0.3-0.5 mg/kg doses where anti-PAR1 effects on platelet aggregation were observed at 30 min-2 h, drug levels of PZ-128 achieved therapeutic concentrations of 1-3 μM (~920-2800 $\mu\text{g/mL}$). Peak drug levels (C_{max}) occurred at the end of the 1 h or 2 h infusion in all dose cohorts with a terminal $t_{1/2}$ of elimination of 1.3-1.8 h. Drug was undetectable in plasma at 24-192 h in all subjects. There was little ($\leq 1-2.6$ ng/mL) or no PZ-128 detected in urine at any time point in all subjects consistent with the notion that the pepducin is not eliminated by the kidneys. The drug concentrations were highly linearly correlated with increasing dose at 0.25-8 h time points with R values of 0.980-0.998. Likewise, AUC and C_{max} of PZ-128 in plasma were linearly correlated with dose.

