All subjects will complete the protocol-specified in-hospital tests, collections, and evaluations up to the time they are discharged from the hospital. The duration of hospitalization will vary depending upon the clinical circumstances (e.g., subject comorbidities, type of procedure(s), complications from procedure(s), and need for further testing /procedures) and local standards

of care and may include same day discharge, overnight stay for observation or inpatient admission.

Prior to discharge from the hospital, the return visit will be scheduled for 14 days (± 5 d) after the administration of the study drug, and follow-up telephone contacts should be scheduled for 30 days (± 5 d) and 90 days (± 7 d) after the administration of the study drug.

Appropriate assessments will be used to characterize the overall effects of PZ-128. In particular, selected center(s) will participate in a sub-study that will include specific testing to assess inhibition of platelet aggregation and the pharmacokinetic/pharmacodynamics (PK/PD) relationship of PZ-128.

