6.3.1 Subject Inclusion Criteria

The subject must meet **all** of the following criteria listed below for entry:

1. The subject is at least 18 years of age and may be of either sex/gender and of any race and ethnicity.
2. The subject is scheduled to undergo non-emergent PCI or non-emergent cardiac catheterization with the intention of performing PCI. The following classifications of the urgency of the procedure at the time the operator decides to perform it will be used for randomization stratification [54]:

a. Elective: The cardiac catheterization procedure \pm PCI can be performed on an outpatient basis or during a subsequent hospitalization without significant risk of MI or death. For stable inpatients, this is a procedure that is performed during the hospitalization for convenience and ease of scheduling only, and not because the subject's clinical situation demands that the procedure be performed prior to discharge.

OR

b. Urgent: The cardiac catheterization \pm PCI procedure should be performed on an inpatient basis and before discharge because of significant concerns about the risk of myocardial ischemia, MI and/or death. For subjects who are outpatients or in the emergency department at the time that the cardiac catheterization is requested, this is a procedure that would warrant hospital admission based on clinical presentation.

3. There is no anticipation that the subject would require treatment with a GP IIb/IIIa inhibitor prior to the initiation of the cardiac catheterization \pm PCI procedure if the subject were not a participant in the current research study, and no anticipation of use during the procedure.
4. The subject is willing and able to give appropriate informed consent and complete all study-related procedures, and able to adhere to dosing and visit schedules (i.e., subject signs an approved informed consent document(s) and provides HIPAA authorization).
5. The subject will undergo all of the pre-enrollment parameters according to **Section 1.2** prior to randomization and have them completed within 14 days prior to the scheduled cardiac catheterization \pm PCI procedure and study drug administration.

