6.4.7.7 Administration

The study drug will be delivered once as a continuous IV infusion using an intravenous infusion pump given over a 2-hour period

This will be a dedicated line for the study drug administration compatible with the institution's IV pump module and will be supplied by the clinical site. PZ-128/placebo will be administered by a qualified member of the study staff or institution's clinical staff following successful enrollment/randomization prior to cardiac catheterization.

Intravenous PZ-128/placebo will be administered peripherally through an intravenous catheter which should not be smaller than 20-gauge. It is recommended that PK/PD/exploratory

biomarkers/pharmacogenomics research samples are obtained from a distal venous site, ideally from the opposite arm or alternatively from a site distal to the site of drug infusion. If a subject has a central line in place, PZ-128/placebo may be administered via that route. If PZ-128/placebo is administered via central venous catheter, it is strongly recommended that PK/PD/exploratory biomarkers/ pharmacogenomics research samples are obtained by peripheral venipuncture if at all possible. Due to the potential overflow volume in the commercial D5W IV bag, the entire contents of the IV bag should be infused for complete dosing.

The investigator or designated medical staff must be present during the administration of the investigational product to assess and treat adverse events that may arise during dosing. Anaphylaxis precautions must be observed during the PZ-128/placebo administration and for at least 1 hour following the completion of the infusion. Subjects will be monitored in the cardiac catheterization lab until discharge or transfer to another hospital unit per the protocol and local standards of care.

There will be no dose modifications or alterations to the rate of infusion. Subjects should receive the entire study drug infusion regardless of whether a PCI is performed. Potential drug allergic reactions that occur during the administration of PZ-128/placebo may necessitate stopping and restarting the infusion (interruption/temporary cessation of the infusion is allowed for up to 1 hour only) or discontinuing (permanent cessation) the study drug infusion, regardless of whether the reaction is deemed related or not-related to PZ-128/placebo (See **Management of Drug Allergic Reactions Section 6.7.2.3**).

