6.6.3.2 Optional

Samples will be collected only from subjects who sign the appropriate section in the consent form(s) for these optional collections and analysis. The time points provided for the collection of blood samples for exploratory biomarkers research, pharmacogenomics and pharmacokinetics/pharmacodynamics-platelet aggregation will be indexed from the start of the PZ-128/placebo infusion (i.e., Time=0).

These blood samples and any other components may be retained by the sponsor for analysis until the study-specific scientific objectives have been completed. The subject retains the right to have the sample material destroyed at any time by contacting the investigator. The sponsor will be the exclusive owner of any data, discoveries, or derivative materials from the sample materials and is responsible for the destruction of the sample(s) at the request of the research subject through the investigator or at the end of the storage period. Following the request from a research subject, the investigator will provide the sponsor with the required study and subject number so that any remaining blood samples and any other components can be located and destroyed. If a commercial product is developed from this research, the sponsor will own the commercial product. The subject will have no commercial rights to such product and will have no commercial rights to the data, information, discoveries, or derivative materials gained or produced from the samples. See **Section 8.2** and **Appendix E** for subject confidentiality.

Subjects at All Centers

- **Exploratory Biomarkers Research (Plasma): Just Prior to Study Drug Infusion, Select Times During Hospitalization, 24-hour/Discharge, 14-day Visit**

Blood samples for exploratory research of systemic markers of thrombosis and platelet reactivity, inflammation, and metabolomics will be collected just before the administration of the study drug, then 2 hours + 15 min (immediately after completion of infusion), 6 hours – 2 h (4 to 6 h) and 24 hours ± 2 h or discharge (whichever occurs sooner) after the start of the study drug infusion and at the 14-day visit. After the 24-hour collection, if a subject remains in the hospital for ≥48 hours, a blood sample will

be collected just prior to discharge. The samples will be analyzed by the sponsor under non-GLP conditions.

- **Pharmacogenomics (DNA and RNA) (Whole Blood): Just Prior to Study Drug Infusion**

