7.9 Other Analyses

7.9.1 Pharmacokinetics

The plasma portion of the blood samples from each consenting participant will be assayed at a centralized lab for PZ-128 under non-GLP conditions at baseline and select time points following the start of the study drug administration as specified in **Section 6.6.3**. PK parameters will be calculated over time (C_{max} , AUC, $t_{1/2}$, Clearance and Distribution) and will be summarized by dose level. Data will be presented using graphical summaries and descriptive statistics.

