7.9.2 Pharmacodynamics

At select sites, blood samples from each consenting participant will be analyzed onsite using Light Transmission Aggregometry (LTA) under non-GLP conditions at baseline and select time points following the start of the study drug administration as specified in **Section 6.6.3**.

The following will be measured:

- Inhibition of platelet aggregation (maximum and final) induced by SFLLRN 5-20 μM (or SFLLRN of equivalent potency) using blood collected in 0.4% sodium citrate.
- Inhibition of platelet aggregation (maximum and final) induced by AYPGKF 160 μM using blood collected in 0.4% sodium citrate.
- Inhibition of platelet aggregation (maximum and final) induced by collagen 4-20 $\mu\text{g/mL}$ using blood collected in 0.4% sodium citrate.
- Inhibition of platelet aggregation (maximum and final) induced by 5-20 μM ADP using blood collected in 0.4% sodium citrate.
- Inhibition of platelet aggregation (maximum and final) induced by thrombin 1 nM-1 μM using blood collected in 0.4% sodium citrate (with GPRP added for 1mM final concentration).

Maximal and final extent inhibition of platelet aggregation (IPA) from pre-dose baseline at Screening will be calculated at all subsequent time points using

$$\text{Percentage of Inhibition} = 100\% \times \frac{(\text{PAs} - \text{PA})}{(\text{PAs})}$$

Where PA is the mean response at the given time point, and PAs is the mean response at pre-dose baseline (Screening). Percentage inhibition will be restricted to the closed interval [0,100]; any data falling outside this range will be truncated to the appropriate limit. Individual peak inhibition of platelet aggregation (IPA_{max}) will be estimated as the highest IPA within the collection time period and TIPA_{max} will be the time to IPA_{max} for final extent and maximum extent of IPA.

The percentage inhibition of the specific agonist-induced platelet aggregation (final and maximum extent) will be summarized at the scheduled protocol time points using standard summary statistics for each treatment group. Mean plots showing changes within treatment groups across time will be presented. The derived PK and PD parameters will be summarized using standard summary statistics and graphical presentations.

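### Platelet-inhibition samples taken at early discharge fall into the 24-hour summary, which can overstate residual inhibition at 24 hours

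*Combined protocol and SAP*

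**What the plan says.** Sampling. Note 12 to the flow chart (Section 1.2) places the last routine in-hospital PD and pharmacokinetic (PK) sample at 24 h ± 2 h after infusion start, "or at hospital discharge, whichever occurs sooner". Note 13 does the same for biomarkers. Section 6.6.3.2 repeats the rule: 24 h ± 2 h "or discharge (whichever occurs sooner) after the start of the study drug infusion and at the 14-day visit". No earliest time is set for the discharge sample. The flow chart, Section 6.5.7 and Table 1 all treat 24 hours and discharge as one visit. Table 1 also counts the extra discharge sample, for stays of 48 h or more, in that same column.

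Discharge. Section 6.1 says the hospital stay "may include same day discharge, overnight stay for observation or inpatient admission". Under Section 6.3.1 an elective procedure is one that "can be performed on an outpatient basis", and Section 6.4.4 caps neither stratum. Anaphylaxis precautions apply during the 2-hour infusion and "for at least 1 hour following the completion of the infusion" (Section 6.4.7.7). That rule alone does not exclude discharge from about 3 h after infusion start.

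Analysis. Section 7.9.2 says percentage inhibition "will be summarized at the scheduled protocol time points using standard summary statistics for each treatment group", and adds mean plots across time. Section 7.9.3 compares biomarker changes descriptively at each later time point. Section 7.9.1 works differently: "PK parameters will be calculated over time" and are summarised by dose level. Section 8.2 requires the collection date and time on the optional samples. Section 7.2 leaves data-handling conventions to a separate SAP.

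**The concern.** A sample labelled 24 hours may have been drawn the same afternoon. In phase 1 the 0.5 mg/kg dose still had a strong effect at 6 h: the aspirin subgroup reached "100% inhibition by 6 h" with 8 µM agonist. Averaging such values with genuine 24-hour values makes platelet function look less recovered than it is.

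Inhibition of aggregation is a listed secondary endpoint (Section 6.7.1.4). Reversible inhibition is part of the drug's rationale (Sections 4.1.1 and 4.2.2), and Section 6.7.2.3 states that at least half of the effect is recovered by about 24 hours. For subjects who leave before 48 h, this slot is the only scheduled PD observation between the 4-6 h sample and the 14-day visit. It is therefore the trial's main direct check on that statement. Section 4.1.2.2 says the study's information will inform whether to proceed to phase 3 and with which regimen.

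**Working it through.** The plan gives no figure of its own to reproduce. The check asks how far the 24-hour mean moves when early samples are mixed in.

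**Inputs from the documents** (Section 4.1.2.2, 0.5 mg/kg)
- Inhibition at 24 h, aspirin subgroup, 8 µM SFLLRN: 40% recovery after complete inhibition at 6 h, read as 60% inhibition.
- Inhibition at 6 h: 60-100% for the 0.5 mg/kg dose, and 100% in the aspirin subgroup at 8 µM. The same subgroup averaged 60-80% at 30 min to 2 h.
- Inhibition at 24 h, aspirin subgroup, 20 µM SFLLRN: 80% recovery, read as 20% inhibition. No 6-hour value is given for 20 µM.

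**Assumptions**
- Share *s* of subjects sampled at same-day discharge: 10%, 30% or 50%. The documents state no share.
- Early inhibition *E*: 60%, 80% or 100%, spanning the 6-hour range. No value between 6 h and 24 h is given, so a late-evening discharge is not covered.
- Subjects who leave early and those who stay share the same time course.

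**Formula**: apparent 24-hour inhibition = (1 − *s*) × *I*24 + *s* × *E*, where *I*24 is the true 24-hour value.

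**8 µM, *I*24 = 60%**

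| *s* | *E* = 60% | *E* = 80% | *E* = 100% |
|---|---|---|---|
| 10% | 60% | 62% | 64% |
| 30% | 60% | 66% | 72% |
| 50% | 60% | 70% | 80% |

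For example, 0.7 × 60 + 0.3 × 100 = 42 + 30 = 72. In terms of recovery, the true 40% would appear as 36-40%, 28-40% and 20-40% for the three shares.

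**20 µM, *I*24 = 20%**, with *E* = 60-100% purely assumed: 0.9 × 20 + 0.1 × (60 to 100) = 24-28%; 0.7 × 20 + 0.3 × (60 to 100) = 32-44%; 0.5 × 20 + 0.5 × (60 to 100) = 40-60%.

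**If true recovery is exactly 50%**, the threshold in Section 6.7.2.3, then *I*24 = 50%. With *E* = 60-100%, apparent inhibition is 51-55%, 53-65% and 55-75% for the three shares. Apparent recovery is then 45-49%, 35-47% and 25-45%. Sample timing alone could make the data seem to contradict the protocol's statement.

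**With the fix** (*s* = 0 within 22-26 h), the phase 1 inputs return 60% inhibition at 8 µM and 20% at 20 µM.

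**The case against.** The strongest reply is that this is an optional, select-site, descriptive sub-study. It tests no hypothesis and bears on neither the primary bleeding endpoint nor the key secondary endpoint. The mixed timing is openly labelled in the flow chart, collection times are recorded, and the separate SAP could still set windows. Randomisation is stratified by site and urgency, so discharge times should be similar across arms.

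Most of that is true, and it limits the importance of the point. It does not remove it. Section 7.9.2 already commits to scheduled time points, and nothing in the documents overrides that. Similar discharge times across arms do not cancel the shift either, because placebo subjects have no PZ-128 effect to recover from.

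Several stronger readings are tempting but unsupported:
- *That PK has the same fault.* No 24-hour PK mean is planned. Plasma peaks at the end of infusion with a half-life of 1.3-1.8 h (Section 4.1.2.2). By 2^(−(t − 2)/t½), levels are about 12-21% of peak at 6 h and 4-10% at 8 h, so a same-day PK sample is not near peak. The effect is a shorter sampled terminal phase.
- *That biomarkers are caught near peak effect.* No biomarker time course is given. Only the time-labelling problem carries over.
- *That comparisons by urgency are confounded.* Section 7.9 plans no PD comparison by urgency.
- *That a formal recovery estimate is biased.* None is named. The plan reports inhibition by time point, plus peak inhibition and time to peak.
- *That early inhibition is always 100%.* That figure comes from the aspirin subgroup of one dose cohort in a study with 31 treated subjects. Section 4.1.2.2 also gives 60-100% at 6 h, and at 60% the shift disappears.

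**Conclusion.** The point holds for the PD summary. The sampling rule, the expected same-day discharges and the scheduled-time summary together put early-discharge samples into the 24-hour IPA mean. With the phase 1 inputs, apparent inhibition at 8 µM would be 60-64%, 60-72% or 60-80% for same-day shares of 10%, 30% or 50%, against 60% without mixing. The direction is towards overstated residual inhibition, or no change at the bottom of the range.

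The size rests on assumed shares, on a small phase 1 subgroup for the 24-hour value, and on 6-hour inhibition standing in for inhibition at discharge. The 60% is a phase 1 reference figure and need not be the true value in this trial. The 0.3 mg/kg dose is not sized because no 24-hour phase 1 value is given for it.

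A reader might infer that pooling is certain to occur. The documents support less than that: it is what the plan as written does, and the separate SAP could still prevent it. The consequence is confined to a descriptive secondary endpoint, but the distortion is avoidable.

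**What to change.** In Section 7.9.2, or in the SAP before unmasking:
- Admit to the 24-hour summary only samples drawn 22-26 h after infusion start, which is the protocol's own ± 2 h window.
- Report earlier discharge samples as a separate category, with its time bounds set in advance.
- Give the discharge sample for stays of 48 h or more its own label.
- Plot IPA against actual collection time, and state how many subjects contribute to each category.

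Apply the same time labels to the biomarker comparisons in Section 7.9.3, and state in Section 7.9.1 that PK parameters are derived from actual sampling times.

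No new sampling or data field is needed, since Section 8.2 already provides for collection date and time. The cost is SAP wording, a little programming and a smaller 24-hour summary. Some samples close to the window, such as those from a discharge at 20-21 h, would leave that summary, but they stay visible in the actual-time plot.
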